6.2 Statistical Analysis

All main analyses will be conducted on an intention-to-treat basis. Models will assess the relationship between the timing of disulfiram treatment initiation relative to symptom onset and study outcomes for key efficacy/activity endpoints. The model will be fitted using generalized estimating equations (GEE) to handle the repeated measurements, where the comparison between randomized arms will use a two-sided Wald test. Levels of plasma inflammatory biomarker levels will be compared between arms using non-parametric Wilcoxon rank-sum tests (e.g., separately on days 5 and 15) considering results below the assay limit as the lowest rank. For the analysis of the SARS-CoV-2 viral loads, for the comparison of the proportion of participants with detectable SARS-CoV-2 RNA, we will use binary regression, with adjustment for risk stratum and pre-treatment SARS-CoV-2 RNA level.

For longitudinal analyses, we will perform both statistical summaries at each time point and comprehensive regression modeling. For the regression model, a full non-linear mixed effects (NMLE) model will be developed for disulfiram including all 60 participants across the 5 dosing days. The pharmacokinetics of disulfiram and the measured metabolites will be described by compartmental models parameterized in terms of clearance from the central compartment, apparent central and peripheral Vd and intercompartmental clearance. This will be followed by a full covariate screening process and then inclusion into the pharmacokinetic model. This may include covariates like drug interactions due to other therapy, weight, sex and other biologically plausible covariates collected during the study. From the final model, we will provide the AUC₀₋₇₂, C_{min}, and C_{max} for each patient.

For the primary pharmacodynamics response (plasma inflammatory biomarker levels – e.g., IL-6) the PK and PD data will be combined and analyzed simultaneously by nonlinear mixed-effects modelling (NONMEM version 7.1, Globomax LLC, Hanover, PA). Data will be analyzed using the first-order conditional estimation method with interaction, and ADVAN6 will be used to solve the differential

equations. Both empiric and mechanistic based pharmacodynamics models will be evaluated to describe the concentration effect relationship with the primary pharmacodynamics response.

Model selection will be based on visual inspection of diagnostic scatter plots, the objective function value (OBJ) computed by NONMEM and biological plausibility of parameter estimates. All final models will be evaluated by performing a visual predictive check (VPC). For this, 1000 data sets will be simulated from the final parameter estimates using the original data as a template. This approach has been successfully applied for the development of animal and human models. From the final model, Monte-Carlo simulations will be undertaken to evaluate if different dosing schedules (e.g. larger doses less often or a single dose) can optimize the dose-concentration-effect relationship.

As this is an exploratory study, we will collect all possible trial outcomes, including those for participants who discontinue treatment. We will attempt to minimize the amount of missing data as much as possible to avoid bias in the interpretability of the findings. However, in the event that missing data is present we will follow standardized methods for handling these data. For time dependent covariates, if one covariate value of a participant is available, this will be carried forward unless the first value of the covariate is missing, then it will be carried backward to occasions with missing values of the respective covariate. The population median value at each time point will be used for missing data from a continuous variable (e.g. age and weight) for a particular participant. If a covariate, which can be classified as a categorical variable (e.g. sex and race), is recorded missing, the observation will be set to the mode. If either race or sex is found significant and there is missing data of the covariate in question in more than 10% of the population, then a sensitivity analysis will be performed, re-estimating the model with and without the covariate only in the participants that have information of the covariate in question. If a large proportion of participants (>15%) have a missing covariate this may be imputed from other covariates. The imputation will be based on a mixed effect linear regression model developed for the highly correlated covariates. Multiple imputation approach will be used to account for uncertainty in missing values. If any value is missing at baseline, screening values may be used for imputation, if available.

From the time to treatment initiation to clinical recovery or improvement, all participants will be censored at the end of follow-up, not at the time of event (e.g., for mortality). Sensitivity analyses will be performed using imputation of missing data to differentiate discontinuation of participants from treatment versus study evaluations.

Duration of fever, duration of symptoms and duration of time to self-reported return to usual health will be summarized with descriptive statistics. Participant-specific durations of fever and symptoms will be compared between study arms using a two-sided stratified Wilcoxon test with a 5% Type I error rate. Total symptom score will be calculated on each day and the participant-specific area under the curve (AUC) over time will also be compared using a two-sided stratified Wilcoxon test. Participants who do not have complete diary cards due to hospitalization or death will be ranked in these analyses as having poorer outcomes than participants who survived without hospitalization.

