5.3.4 Treatment

A total of 60 participants will be randomized (2:1) to receive active drug versus placebo in a dose escalation study. The first 30 participants will be enrolled in the 1000 mg dosing cohort, randomized 2:1 to receive either disulfiram 1000 mg (N=20) or placebo (N=10) daily for 5 consecutive days. As long as safety monitoring criteria are met to proceed to the second dose, the next 30 participants will be enrolled in the 2000 mg dosing cohort, randomized 2:1 to receive either disulfiram 2000 mg (N=20) or placebo (N=10) daily for 5 consecutive days.

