5.3.5 Randomization

Participants enrolled in the study will be randomized using a web-based randomization procedure to receive active drug or no therapy at a 2:1 ratio within each dosing cohort.

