6 STATISTICAL PLAN

6.1 Sample Size and Power Considerations

Based on a design with 20 patients per disulfiram treatment group within each dosing cohort (1000 mg, 2000 mg) and a null hypothesis that there will be a differential change in plasma inflammatory cytokine levels (e.g., IL-6) in both groups (disulfiram treatment and placebo compared to baseline), we use reported ranges of plasma IL-6 levels in COVID-19 disease¹¹⁹ to estimate sample size and power. Based on a mean plasma IL-6 level of 36.7 pg/mL (95% CI 21.6-62.3 pg/mL), we estimate that the study will have approximately 80% power to detect a 35% difference in plasma IL-6 levels between the disulfiram versus placebo groups. These measurements will be assessed at day 5, 15 and 31 at the 0.05 significance level using a log-likelihood ratio test and non-linear mixed effect regression modeling. This estimate is based on the assumptions that plasma IL-6 levels are log normally distributed and that the standard deviation of the pre- and post-dose levels is 12 ng/mL (derived from ref: DE Leisman et al. Cytokine elevation in severe and critical COVID-19: a rapid systematic review, meta-analysis, and comparison with other inflammatory syndromes). The adjustments will be made for pre-treatment plasma inflammatory cytokine (e.g., IL-6) levels. Safety endpoints will include the total number of Grade 2 or higher events; the number of Grade 2 or higher events possibly, probably or definitely related to study drug; the number of serious adverse events; and the number and cause for treatment or study discontinuation.

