8.1 Criteria for Discontinuation of the Study

Two cohorts of participants (N=30 each) will be sequentially enrolled and receive disulfiram daily for five days at doses of 1000mg or 2000mg. The independent Safety Monitoring Committee will review the safety and tolerability data after the first cohort has completed dosing and determine whether it is safe to proceed with enrolling the final cohort using the below criteria.

In addition, the study enrollment and dosing will be stopped and an ad hoc review by the SMC will be performed if any of the specific following events occur or, if in the judgment of the study physician, participant safety is at risk of being compromised:

- a. Death within one hour of drug administration
- b. Occurrence of a life-threatening allergic/hypersensitivity reaction (anaphylaxis), manifested by bronchospasm with or without urticaria or angioedema requiring hemodynamic support with pressor medications or mechanical ventilation, TRALI, TACO.
- c. One participant with an SAE associated with study product.
- d. Two participants with a Grade 3 or higher lab toxicity for the same parameter associated with study product. (Grading will be assessed using DAIDS Toxicity Table <https://rsc.niaid.nih.gov/sites/default/files/daidsgradingcorrectedv21.pdf>)
- e. An overall pattern of symptomatic, clinical, or laboratory events that the SMC considers associated with study product and that may appear minor in terms of individual events but that collectively may represent a serious potential concern for safety.
- f. Any other event(s) which is considered to be a serious adverse event in the good clinical judgment of the responsible physician. This will be appropriately documented.

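### Section 6.2 adjusts for an undefined risk stratum, names no strata for its stratified tests, and never uses dosing cohort, the one factor randomized within

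*Combined protocol and SAP*

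**What the plan says.** **Allocation.** Section 5.3.5 randomizes "at a 2:1 ratio within each dosing cohort" and names no other factor. Section 5.3.4 puts the first 30 participants in the 1000 mg cohort, "randomized 2:1 to receive either disulfiram 1000 mg (N=20) or placebo (N=10)"; if safety criteria are met, "the next 30 participants will be enrolled in the 2000 mg dosing cohort" with the same 20:10 split. Section 8.1 confirms the order: "Two cohorts of participants (N=30 each) will be sequentially enrolled".

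**Adjustment and strata.** In section 6.2 the analysis of detectable viral RNA is a binary regression "with adjustment for risk stratum and pre-treatment SARS-CoV-2 RNA level". The term risk stratum occurs nowhere else. Durations of fever and symptoms are compared by a "two-sided stratified Wilcoxon test with a 5% Type I error rate", and the area under the symptom-score curve by a stratified Wilcoxon test as well. Neither names its strata. For the primary biomarker, section 6.1 says "The adjustments will be made for pre-treatment plasma inflammatory cytokine (e.g., IL-6) levels".

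**Cohort.** The GEE/Wald, rank-sum and binary regression analyses (6.2), Fisher's test (6.2.4) and quantile regression (6.2.5) compare arms. They do not say whether that means drug against placebo, each dose against its own placebo, or each dose against all placebo. None has a cohort term. The non-linear mixed-effects model in 6.2 is to include all 60 participants; its possible covariates do not name cohort.

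**The concern.** Two of the specified analyses cannot be run as written without a choice made later. The regression needs a variable that the documents do not define, and the Wilcoxon tests need strata that they do not name. In an exploratory trial of 60 participants, choosing these after the data are seen is avoidable.

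The factor left out is the one that the design supports. The two placebo groups of 10 are recruited in different periods, and section 5.3.8 permits whatever is standard of care at the site, including antivirals under emergency authorization. Background treatment can therefore change between cohorts. An analysis that combines cohorts without a cohort term then either loses precision or, for some contrasts, mixes dose with calendar time.

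**Working it through.** **1. The plan's power figure.** Inputs from section 6.1: mean IL-6 36.7 pg/mL, difference 35%, two-sided 0.05, SD 12. The SD is printed in ng/mL and read here as pg/mL, which is an assumption. The difference is 0.35 × 36.7 = 12.845. With power = Φ(difference/SE − 1.96):

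- 20 v 10, SD 12: SE = 12 × √(1/20 + 1/10) = 4.648; 12.845/4.648 = 2.764; power 0.789.
- 20 v 20 (one dose v all placebo), SD 12: power 0.923.
- 40 v 20, SD 12: power 0.974.
- 40 v 20, change-score SD 12√2 = 16.97: SE = 16.97 × √(1/40 + 1/20) = 4.648; power 0.789.
- 20 v 10, SD 16.97: SE = 6.573; ratio 1.954; power 0.498.

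The stated 80% fits a within-cohort comparison with concurrent placebo, which matches section 6.1's framing by dosing cohort. It fits a pooled comparison on change scores equally well, so the match does not settle the comparator.

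**2. Effect of a cohort shift.** Let cohort 2 differ from cohort 1 by d SD for reasons other than drug. The documents give no value; d from 0.25 to 1.0 is assumed.

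- *2000 mg v all placebo:* expected difference d − (10·0 + 10·d)/20 = d/2. For 1000 mg it is 0 − d/2 = −d/2.
- *All active v all placebo:* both arms have half their participants in each cohort, so the bias is 0. Omitting cohort inflates the SD by √(1 + d²/4), which is 1.03 at d = 0.5 and 1.12 at d = 1.0. At d = 1.0 the effective critical value is 1.96 × 1.118 = 2.19, a type I error of 0.028.
- *Each dose v its own placebo:* the shift cancels.

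**3. Exposure-response stand-in.** A null outcome was regressed on a straight-line exposure term in all 60 participants. Exposure was set to the median parent-drug AUCs in section 4.1.7, Table 1 (8,386 at 1000 mg and 22,331 at 2000 mg), with placebo at 0.

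Simulated type I error, no drug effect, no baseline adjustment (repeat runs agree to about 0.01):

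| Shift d (SD) | 40 v 20, no cohort | 2000 mg v all placebo | Linear exposure, no cohort | 2000 mg v own placebo |
|---|---|---|---|---|
| 0.25 | 0.047 | 0.066 | 0.073 | 0.050 |
| 0.50 | 0.045 | 0.112 | 0.148 | 0.051 |
| 0.75 | 0.036 | 0.191 | 0.268 | 0.050 |
| 1.00 | 0.028 | 0.300 | 0.411 | 0.049 |

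With a cohort term, the exposure model stays at about 0.05 throughout.

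The exposure result depends on the shape of the response. With a saturating curve and the AUC50 of 1,600 quoted in section 4.1.7, the two doses give 8,386/9,986 = 0.84 and 22,331/23,931 = 0.93 of the maximum. Exposure then acts almost as a drug indicator, and no inflation appears.

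**4. Cost in precision.** A model with two dose terms plus cohort has the same standard-error factor as the concurrent contrast: √(1/20 + 1/10) = 0.387.

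**The case against.** The strongest reply is that the documents never plan the biased contrast. A reader might infer that each dose will be tested against all 20 placebo participants. No text says so: the objectives pair each dose with its cohort, randomization is within cohort, and section 6.1 is framed within cohort. That stands. The comparator is unstated, and the dose-specific bias is conditional on a choice left open.

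A reader might also infer that the analyses in general adjust for a risk stratum. Only one secondary analysis does. Nor is the pooled drug-versus-placebo test invalid: it is unbiased and loses only precision.

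Baseline adjustment is a further defence. The primary endpoint is change and section 6.1 adjusts for the pre-treatment level, so part of any shift present before treatment would be removed. This also stands, but the rank-sum tests of biomarker levels and the Wilcoxon tests of durations have no such adjustment as described.

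The size on the IL-6 scale is uncertain too. Section 6.1's own figures imply a log SD of √ln(1 + (12/36.7)²) = 0.319. Shifts of 0.5 and 1.0 SD would then bias the dose-versus-all-placebo ratio by exp(0.25 × 0.319) − 1 = 8% and exp(0.5 × 0.319) − 1 = 17%. A larger log SD would give more.

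Finally, the synopsis plans stratified analyses by symptom severity and baseline laboratory values, so the risk stratum may have been meant as one of these. The text does not make that link and gives no categories. This argues for asking the sponsor to define the term rather than assuming it meant cohort.

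**Conclusion.** The point holds in this form: one secondary regression adjusts for an undefined variable, the stratified Wilcoxon tests lack named strata, and dosing cohort is in no analysis although it is the only factor randomized within. This should be corrected.

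The statistical cost rests on an assumed drift between cohorts. For shifts of 0.25 to 1.0 SD without baseline adjustment, the pooled test is conservative (about 0.05 down to 0.03), a dose-versus-all-placebo contrast has type I error of about 0.07 to 0.30, and a linear exposure model on all 60 participants about 0.07 to 0.41. The last depends on the response shape, which section 6.2 leaves to model selection. The documents do not support saying that the planned dose contrasts are biased; they support saying that the plan does not rule it out. Changing standard of care is the only source of drift with a basis in the text.

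**What to change.** In section 6.2:

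- Adjust the binary regression for dosing cohort and pre-treatment RNA. Delete the risk stratum, or define it from a baseline variable already collected, with its categories.
- Name dosing cohort as the stratum in both Wilcoxon analyses when cohorts are combined.
- State that each dose is compared with its own cohort's placebo.
- Include a cohort term in any model that uses both placebo groups, including the 60-participant PK/PD model.

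Cohort is already recorded, so only SAP wording changes. The sponsor should confirm which comparison the 80% power describes. The 20 v 10 contrast has about 79% power if the SD of 12 pg/mL applies to it directly, but about 50% if the figure came from 40 v 20 with a change-score SD of 12√2.

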- Current use of oral lopinavir/ritonavir solution (and the inability to switch to a solid dosage form during the entire duration of the study).
- Current use of warfarin.
- ALT or AST > 2 x the upper limit of normal or total bilirubin outside the normal range.

	
 • Creatinine clearance (CrCl) < 50 mL/min by Cockcroft-Gault. • Allergy to rubber or thiuram derivatives
TEST PRODUCT, DOSE, AND ROUTE OF ADMINISTRATION	
Oral disulfiram given as 1000 mg daily (cohort 1) or 2000 mg daily (cohort 2) versus placebo for 5 consecutive days in adults with early symptomatic SARS-CoV-2 infection will be administered in a double-blind fashion.
 
Placebo tablets will be administered in a double-blind fashion and given as a single oral administration on days 1-5.

DURATION OF PARTICIPATION AND DURATION OF STUDY	
Study products will be administered at days 1-5. Participants will be observed on study at days 5, 15, and 31.
 
Participants will be randomized to either of two treatment arms, oral disulfiram or placebo.
 
Screening: up to 7 days prior to treatment randomization.
 
Treatment (for each arm): 5 days (participants to be observed for a total of 4 hours on the last treatment day, Day 5)
 
Follow-up (for each arm): 31 days after the initial dose for that treatment arm.
 
The total duration of the study is expected to be 31 days (approximately 1 month).

CONCOMITANT MEDICATIONS	
The following medications are not allowed during the study because of potential interactions with disulfiram: warfarin; any over the counter drug, food or other product that contains or might contain alcohol; if HIV-positive, specific protease inhibitor preparations (oral amprenavir solution, ritonavir solution, lopinavir/ritonavir solution, soft gelatin form of ritonavir or lopinavir/ritonavir, tipranavir).

EFFICACY EVALUATIONS	
 • Change in plasma inflammatory biomarker levels² • Change in SARS-CoV-2 viral load⁴ • Change in COVID-19 symptom severity³ (5-point scale)
PRIMARY ENDPOINTS	
 • Change in plasma inflammatory biomarker levels² (e.g., IL-6, IL-1β) at days 5, 15, and 31.

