SECONDARY ENDPOINTS	
 • Safety and tolerability • Change in SARS-CoV-2 PCR quantitative viral load⁴ at days 5, 15, and 31. • Change in COVID-19 clinical stage (five-point symptom severity scale³) at days 5, 15, and 31. • Time to recovery (date of symptom onset to date of complete resolution of symptoms) • If applicable, the proportion of participants hospitalized at day 5, 15, and 31. • If applicable, the proportion of participant deaths at day 5, 15, and 31
OTHER EVALUATIONS	
 • SARS-CoV-2 specific T- and B- cell responses⁵ • Pyroptosis (aberrant proinflammatory cell death) assay⁶ • High sensitivity SARS-CoV-2 antibody titer (IgM, IgE, IgA, IgG1, IgG2, IgG3, IgG4) • Changes in host gene and protein expression from matched blood and respiratory (NP) samples at the single cell level (B, T, natural killer, and myeloid cells). • Changes in T- and B-cell receptor (TCR/BCR) repertoire from matched blood and respiratory (nasal/oropharyngeal) samples.
SAFETY EVALUATIONS	All participants will be followed for possible adverse events (AEs) throughout their involvement in the study.
PLANNED INTERIM ANALYSES	A Safety Monitoring Committee (SMC) will be convened and will meet biannually to review all adverse events and the conduct of the study. Serious adverse events will be monitored by the committee on an ongoing basis throughout the study. All main analyses will be conducted on an intention-to-treat basis. Models will assess the relationship between the timing of disulfiram treatment initiation relative to symptom onset and study outcomes for key efficacy/activity endpoints. Stratified analyses will be performed based on symptom severity, as well as laboratory values (e.g., hs-CRP, ferritin, D-dimer levels at baseline).

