5.2 Study Definitions

- *Enrolled*: From time consented to participate until designated as (i) ineligible based on the inclusion/exclusion criteria or withdraws, (ii) been discontinued from the study or (iii) completed the study.
- *Randomized*: when a randomization number is assigned.
- *Screen Failures*: signed informed consent, but then determined to be ineligible or withdraws before being randomized.
- *Discontinued*: randomized, but then withdrawn by investigator or participant withdraws consent.
- *Completed*: Participants are considered completed when they are followed through to day 31, had an adverse event or death occurred prior to day 31.

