5.3.3 Participant Withdrawal

Participants can terminate study participation and/or withdraw consent at any time without prejudice. Randomized participants who withdraw from the study will not be replaced. If a participant discontinues study dosing (for example, as a result of an AE), every attempt should be made to keep the participant in the study and continue to perform the required study-related follow-up and procedures (see Section 8.1, Criteria for Discontinuation of Study Treatment). The investigator may withdraw participants if they are non-compliant with study procedures or if the investigator determines that continued participation in the study would be harmful to the participant or the integrity of the study data.

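### Section 6.2 gives one censoring date for time to recovery, the end of follow-up, and no separate date for participants who withdraw or are lost before recovering

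*Combined protocol and SAP*

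**What the plan says.** The synopsis lists as a secondary endpoint "Time to recovery (date of symptom onset to date of complete resolution of symptoms" (closing bracket omitted). Section 6.2 sets the censoring rule for time from treatment initiation to recovery or improvement: "all participants will be censored at the end of follow-up, not at the time of event (e.g., for mortality" (closing bracket omitted). The synopsis fixes the period as a common one: "Follow-up (for each arm): 31 days after the initial dose for that treatment arm".

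The plan expects departures. Section 5.3.3 states "Participants can terminate study participation and/or withdraw consent at any time without prejudice", lets the investigator withdraw participants, and adds "Randomized participants who withdraw from the study will not be replaced". Section 5.2 defines a discontinued participant as "randomized, but then withdrawn by investigator or participant withdraws consent".

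Stopping treatment is kept apart from leaving the study. For those who stop dosing, section 5.3.3 asks that "every attempt should be made to keep the participant in the study and continue to perform the required study-related follow-up and procedures", and sections 6.2 and 8.2 agree. Directly after the censoring rule, section 6.2 adds "Sensitivity analyses will be performed using imputation of missing data to differentiate discontinuation of participants from treatment versus study evaluations".

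**The concern.** Death and loss to follow-up differ for a recovery endpoint. A participant who has died cannot recover, so keeping that person in the risk set to Day 31 as not recovered is right. A participant who leaves while ill may recover the next week, but nobody will see it: recovery is known only through the diary, the calls and the visits, and these have stopped. Someone who withdraws unrecovered on Day 7 and is censored on Day 31 contributes 31 − 7 = 24 days of apparent non-recovery with no assessment in them.

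The stakes are an understated recovery rate in each arm with such losses, some dilution of a true benefit, and a distorted comparison if loss from the study differs between arms. There is also a choice between two readings of the rule, and that should not be left until the data are unblinded.

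**Working it through.** **Step 1: what the phrase can mean.** For a death, the end of follow-up cannot be the participant's own last contact, because the rule expressly moves the date away from the event. It must be the common end, Day 31. The same words govern all participants.

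**Step 2: whether another date is given.** It is not.
- The detailed missing-data rules in section 6.2 concern covariates.
- The worst-rank rule for incomplete diary cards covers hospitalization or death only, and belongs to the Wilcoxon comparisons.
- The sensitivity analysis names imputation but no method.

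**Step 3: size within an arm.** The plan has no figure for this endpoint to reproduce; its only power statement concerns IL-6. It also gives no recovery or loss rate, so these inputs are assumed: exponential recovery with median 10 days (λ = ln 2/10 = 0.0693 per day), time counted from first dose, horizon 31 days, and a fraction q = 5% to 20% lost independently of recovery. True Day 31 recovery is 1 − e^(−31λ) = 88.3%.

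*Loss spread over 31 days.* Let μ = −ln(1 − q)/31, k = λ + μ, F = 1 − e^(−31k). Then:
- observed recoveries = λF/k
- person-days to own last contact = F/k
- extra days from holding losses to Day 31 = μ(31/k − F/k²)

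For q = 10%: μ = 0.00340, k = 0.0727, F = 0.895. Recoveries are 0.853 per participant, own person-days 12.31 and extra days 0.874. Censoring at last contact gives 0.853/12.31 = 0.0693, the true rate. The literal rule gives 0.853/(12.31 + 0.874) = 0.0647, a ratio of 0.934.

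*Loss uniform over Days 2 to 15.* Let R0 = 0.883 be recovery by Day 31, and R1 = 1 − (e^(−2λ) − e^(−15λ))/(13λ) = 0.426 the recovery seen among those with a loss time. Let E = 13.5 be the mean extra days per such participant, that is, the average of (31 − c)e^(−λc) over c from 2 to 15. For q = 10%, recoveries are 0.9 × 0.883 + 0.1 × 0.426 = 0.838, and person-days are 0.838/0.0693 + 0.1 × 13.5 = 13.4. The rate is 0.0624, a ratio of 0.900.

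| Loss q | Spread over 31 days: Day 31 recovery | Rate ÷ true | Days 2–15: Day 31 recovery | Rate ÷ true |
|---|---|---|---|---|
| 5% | 86.8% | 0.967 | 86.1% | 0.949 |
| 10% | 85.3% | 0.934 | 83.8% | 0.900 |
| 20% | 82.1% | 0.868 | 79.2% | 0.809 |

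For medians of 7 to 21 days with spread loss, the rate is understated by about 3% to 14% and Day 31 recovery by 1.4 to 6.2 percentage points.

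**Step 4: comparison between arms.** A Cox simulation (300,000 participants, 2:1 allocation, spread loss, control median 10 days) gave, under the literal rule:
- Equal loss of 10% or 20%: a true ratio of 1.0 stays at about 1.0; a true 1.5 becomes 1.46 or 1.44.
- Loss of 20% on disulfiram and 5% on placebo: a true 1.0 becomes 0.91; a true 1.5 becomes about 1.3.

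The person-day rates in the table agree for the unequal null case: 0.868/0.967 = 0.90 with spread loss, and 0.809/0.949 = 0.85 with loss on Days 2 to 15. Censoring at last contact returned the true ratios to within simulation error.

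**The case against.** The sentence contrasts the end of follow-up with the time of an event, and its one example is death. It can be read as a rule for competing events only, with a lost participant's end of follow-up being that person's own last contact. This stands as a possible intention. The text does not say so, however, and the same phrase would then carry two meanings in one sentence.

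A reader might infer that poorer tolerability of disulfiram would show up as slower recovery. The documents do not support that. Participants who stop dosing stay in follow-up under sections 5.3.3, 6.2 and 8.2, so intolerance alone does not create a loss. Only leaving the study matters, and nothing in the documents indicates that this will differ by arm. All 30 participants completed the earlier dose-escalation trial described in section 4.1.8, so loss may be low.

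The imputation sensitivity analysis in the next sentence addresses this very distinction. It could expose the effect, but it is unspecified and secondary.

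Scale also counts. The endpoint is secondary, it is missing from the list in section 6.2.2, and the study calls itself exploratory. With about 88% of 40 and of 20 participants recovering (35 and 18 events), the standard error of the log rate ratio is √(1/35 + 1/18) = 0.29. The null shifts to 0.90 and 0.85 are 0.11 and 0.16 on the log scale, or about 0.4 and 0.6 of a standard error. Section 6.2 also names no model for this endpoint, so the person-day rate is an illustration and not the plan's own estimate.

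**Conclusion.** The concern holds as a gap in the censoring rule that should be closed. Taken literally, the rule counts unobserved time as observed non-recovery for participants lost before recovering, and no other date is given for them. With a 10-day median and 5% to 20% loss, the recovery rate is understated by about 3% to 13% (loss spread over 31 days) to 5% to 19% (loss on Days 2 to 15). These sizes rest on assumed rates and on loss being independent of recovery. If participants leave because they are worsening, holding them as not recovered would be nearer the truth. With no loss before recovery there is no bias.

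Two stronger readings go too far. Not every loss is treated like a death: a participant lost after recovering already has an event and is unaffected. Nor is it settled that the authors meant Day 31 for losses; it is what the wording says when taken literally. The comparison between arms is nearly unbiased under the null with equal loss, and a real benefit is modestly diluted. It is materially biased only if loss from the study differs by arm.

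**What to change.** In section 6.2, replace the sentence with a rule in two parts. Participants who die before recovery are censored at Day 31 as not recovered. Participants who withdraw, are withdrawn, or are lost before recovery are censored at their last contact with known symptom status.

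Two related clarifications belong with it. State the imputation method for the planned sensitivity analysis, since that is where loss related to worsening can be examined. Settle the time origin as well: section 6.2 starts the clock at treatment initiation, while the synopsis starts it at symptom onset.

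The main change costs one sentence and needs no new data. If the authors always meant last contact for losses, it only states their intention. It should be made before unblinding, because choosing between the readings afterwards could change the estimate.
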